### 2.2 Secondary

- a) SO 1: To compare proportions of participants exclusively receiving guideline-concordant antibiotic therapy for the entire episode, by EHR-based decision support or usual care.
- b) SO 2: To compare proportions of participants receiving any guideline-concordant antibiotic therapy during the first 24 hours of care, by EHR-based decision support or usual care.
- c) SO 3: To compare proportions of participants receiving any guideline-concordant antibiotic therapy for the entire episode, by EHR-based decision support or usual care.
- d) SO 4: To compare proportions of participants having ED revisits and hospitalizations within 72 hours of the index discharge, by EHR-based decision support or usual care.
- e) SO 5: To compare proportions of participants having ED revisits and hospitalizations within 7 days of the index discharge, by EHR-based decision support or usual care.

### 2.3 Exploratory

- a) EO 1: To compare time to first antibiotic, by EHR-based decision support or usual care.
- b) EO 2: To compare the proportion of participants not receiving antibiotics during the first 24 hours of care, by EHR-based decision support or usual care.
- c) EO 3: To compare the proportion of participants not receiving antibiotics for the entire episode, by EHR-based decision support or usual care.
- d) EO 4: To compare the changes in antibiotics, used as a proxy for treatment failure, after 72 hours, by EHR-based decision support or usual care.
- e) EO 5: To compare the proportion of death, by EHR-based decision support or usual care.

- f) EO 6: To compare the proportion of delayed ICU transfer among hospitalized children, by EHR-based decision support or usual care.

### **3 PROTOCOL OBJECTIVES FOR PHASE 2**

#### **3.1 Primary**

- a) PO 1: To compare proportions of appropriate overall site of care disposition with or without EHR-based prognostic decision support in children with emergency care aged 0.6-17 years.

#### **3.2 Secondary**

- a) SO 1: To compare proportions of appropriate site of care disposition, by EHR-based prognostic decision support or usual care.
- b) SO 2: To compare proportions of participants having ED revisits and hospitalizations within 72 hours of the index discharge, by EHR-based prognostic decision support or usual care.
- c) SO 3: To compare proportions of participants having ED revisits and hospitalizations within 7 days of the index discharge, by EHR-based prognostic decision support or usual care.

#### **3.3 Exploratory**

- a) EO 1: To compare the proportion of death, by EHR-based prognostic decision support or usual care.
- b) EO 2: To compare hospital length of stay among hospitalized children, by EHR-based prognostic decision support or usual care.

### **4 STUDY OUTCOME MEASURES FOR PHASE 1**

#### **4.1 Primary**

- a) POM 1.1: Proportions of participants exclusively receiving guideline-concordant 1st line antibiotic therapy during the first 24 hours of care, by EHR-based decision support. Please see Appendix 1 for the concordant use definitions for 1st line antibiotics.

#### **4.2 Secondary**

- a) SOM 1.1: Proportions of participants exclusively using of concordant antibiotic therapy for the entire episode, by EHR-based decision support or usual care.
- b) SOM 2.1: Proportions of participants using any of concordant antibiotic therapy during the first 24 hours of care, by EHR-based decision support or usual care.
- c) SOM 3.1: Proportions of participants using any of concordant antibiotic therapy for the entire episode, by EHR-based decision support or usual care.
- d) SOM 4.1: Proportions of participants having ED revisits within 72 hours of the index discharge (the enrollment ED visit or hospitalization through discharge), by EHR-based decision support or usual care.  
SOM 4.2: Proportions of participants having hospitalizations within 72 hours of the index discharge, by EHR-based decision support or usual care.

- e) SOM 5.1: Proportions of participants having ED revisits within 7 days of the index discharge, by EHR-based decision support or usual care.  
SOM 5.2: Proportions of participants having hospitalizations within 7 days of the index discharge, by EHR-based decision support or usual care.

#### **4.3 Exploratory**

- a) EOM 1.1: Time to first antibiotic, by EHR-based decision support or usual care.
- b) EOM 2.1: Proportion of participants lacking of antibiotics during the first 24 hours of care, by EHR-based decision support or usual care.
- c) EOM 3.1: Proportion of participants lacking of antibiotics for the entire episode, by EHR-based decision support or usual care.
- d) EOM 4.1: Proportion of participants with different antibiotic(s) or changing treatments from no-antibiotic(s) to antibiotic(s), used as a proxy for treatment failure, after 72 hours, by EHR-based decision support or usual care.
- e) EOM 5.1: Proportion of death, by EHR-based decision support or usual care.
- f) EOM 6.1: Proportion of delayed ICU transfer (>24 hours following hospitalization) among hospitalized children, by EHR-based decision support or usual care.

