1.0 Background

Pneumonia is the most common serious infection in childhood. In the United States (US), pneumonia accounts for 1-4% of all emergency department (ED) visits in children (3-28 per 1,000 US children per year)¹ and ranks among the top 3 reasons for pediatric hospitalization with >100,000 hospitalizations per year (15-22 per 100,000 US children per year)²⁻⁵. Pneumonia also accounts for more days of antibiotic use in US children’s hospitals than any other condition.⁶

Safely reducing inappropriate antibiotic use is critical to slow the progression of antimicrobial resistance, and childhood pneumonia is a key area where substantial improvements can be made. In the 2011 Pediatric Infectious Diseases Society/Infectious Diseases Society of America (PIDS/IDSA) pneumonia guideline, appropriate use of antibiotics was an important area of emphasis.⁷ For presumed bacterial pneumonia, recommendations emphasize the use of a single, narrow-spectrum antibiotic (i.e. amoxicillin or ampicillin). In children <6 years of age treated in the outpatient setting, the guideline recommended considering withholding antibiotics, recognizing that pneumonia in this population is most often caused by viruses. Both of these recommendations were graded as strong and supported by high-quality evidence.⁸⁻¹⁰ Nonetheless, in a large database study we conducted just prior to release of the 2011 guideline, use of broad-spectrum antibiotics was very common among children hospitalized with pneumonia, with substantial differences in antibiotic selection patterns among the various hospitals.¹¹ In that study, use of narrow-spectrum ampicillin was rare (<5%). High rates of broad-spectrum antibiotic use were also noted in a study of children with pneumonia treated and released from US EDs, with <30% of children receiving narrow-spectrum therapy.¹²

Emergency care for childhood pneumonia, including hospitalization rates, varies widely across the nation. A study examining hospital admission rates at 35 US children’s hospitals from 2009-12 showed marked differences in severity-adjusted pneumonia hospital admission rates (median 31%; range 19-69%)¹³. Extending these findings, Florin et al. detected great hospital-level variation in the use of diagnostic tests for children presenting to the ED with pneumonia.¹⁴ They reported that high test-utilizing hospitals had a

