7.0 Study Procedures

7.1 EHR-based Antibiotic Decision Support (P1)

For enrolled subjects assigned to the decision support arm, providers will receive antibiotic recommendations in accordance with the 2011 PIDS/IDSA guideline, tailored to site of care and illness severity. For instance, in young children with mild illness being discharged from the ED, the support tool will offer guidance regarding when a strategy of watchful waiting might be favored over empiric amoxicillin (e.g., fully immunized toddler with upper respiratory tract symptoms). Similarly, in those being admitted to a general ward, the tool will advise consideration of oral therapy in children with good oral intake, or when to consider adjunctive therapy with a macrolide or anti-staphylococcal antibiotic. *Importantly, the tool will offer treatment recommendations only and will not proscribe a specific treatment plan.* If a provider chooses to prescribe therapy not in accordance with the national guideline, the tool will query providers regarding reasons for discrepant prescribing for later analysis.

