7.2 Outcomes (P1)

The primary outcome is the proportion of children exclusively receiving guideline-concordant 1st line antibiotic therapy during the first 24 hours of care (Table 1). For patients discharged from the ED, this will include antibiotics received in the ED as well as antibiotic

Table 1. Concordant Use Definitions for 1st Line Antibiotics¹

Disposition	<6 Years of Age	≥6 Years of Age
Home care	No antibiotics or amoxicillin	Amoxicillin
Inpatient, ward	Ampicillin/amoxicillin	Ampicillin/amoxicillin
Inpatient, ICU or complicated disease ²	Ampicillin or ceftriaxone +/- anti-staphylococcal +/- macrolide	Ampicillin or ceftriaxone +/- anti-staphylococcal +/- macrolide

ICU, intensive care unit ¹Unless specific pathogen identified or known drug allergy ²eg, empyema

prescriptions provided at discharge. For hospitalized patients, this will include therapy received during the first 24 hours of care beginning with ED triage. A patient following treatment according to table 1 will be considered as concordant, whereas deviations from these treatments will be considered discordant.

Secondary outcomes include exclusive use of concordant antibiotic therapy for the entire episode, any use of concordant antibiotic therapy during the first 24 hours of care and for the entire episode, and ED revisits and hospitalizations within 72 hours and 7 days of the index discharge. Index visit is defined as the enrollment ED visit or hospitalization through discharge.

Exploratory outcomes include time to first antibiotic, lack of antibiotics during the first 24 hours of care and for the entire episode, and changes in antibiotics after 72 hours, and death, and for hospitalized children, delayed ICU transfer, defined as >24 hours following hospitalization.

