### 10.3 Exploratory Objectives

There are six exploratory objectives for this study.

- a) The first exploratory objective (EO 1) is to compare time to first antibiotic, by EHR-based decision support or usual care.

The Wilcoxon rank-sum test will be used to compare time to first antibiotic between intervention and control arms.

A frailty regression model will be conducted. The outcome is time to first antibiotic and participants not receiving antibiotics shall be censored at discharge. The covariates under the consideration will be similar to the ones listed in the primary objective analysis 10.1.

- b) The second exploratory objective (EO 2) is to compare the proportion of participants not receiving antibiotics during the first 24 hours of care, by EHR-based decision support or usual care.

Proportions of participants not receiving antibiotics during the first 24 hours of care (yes or no) will be compared between intervention and control arms using a Chi-square test. Proportions and difference of proportions between intervention and control arms will be reported along with their 95% CIs.

A mixed effects logistic regression model will be conducted. The outcome is lacking of antibiotics during the first 24 hours of care (yes or no) and covariates under the consideration will be similar to the ones listed in the primary objective analysis 10.1.

- c) The third exploratory objective (EO 3) is to compare the proportion of participants not receiving antibiotics for the entire episode, by EHR-based decision support or usual care.

The analysis is similar to exploratory objective 2 though the proportion of lacking of antibiotics for the entire episode is the outcome.

- d) The fourth exploratory objective (EO 4) is to compare the changes in antibiotics, used as a proxy for treatment failure, after 72 hours, by EHR-based decision support or usual care.

The analysis is similar to exploratory objective 2 though the proportion of participants with different antibiotic(s) or changing treatments from no-antibiotic(s) to antibiotic(s) after 72 hours is the outcome.

- e) The fifth exploratory objective (EO 5) is to compare the proportion of death, by EHR-based decision support or usual care.

The analysis is similar to exploratory objective 2 though the proportion of death is the outcome.

- f) The sixth exploratory objective (EO 6) is to compare the proportion of delayed ICU transfer among hospitalized children, by EHR-based decision support or usual care.

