NO	YES	NO	NO	YES	Clindamycin	Clindamycin	Clindamycin or Levofloxacin	Levofloxacin	Levofloxacin plus Vancomycin
NO	YES	NO	YES	NO	n/a	Levofloxacin plus Clindamycin or Vancomycin	Levofloxacin plus Clindamycin or Vancomycin	Levofloxacin plus Vancomycin	Levofloxacin plus Vancomycin
NO	YES	NO	YES	YES	n/a	Levofloxacin plus Clindamycin or Vancomycin	Levofloxacin plus Clindamycin or Vancomycin	Levofloxacin plus Vancomycin	Levofloxacin plus Vancomycin
NO	YES	YES	NO	NO	n/a	Clindamycin	Levofloxacin plus Clindamycin or Vancomycin	Levofloxacin plus Clindamycin or Vancomycin	Levofloxacin plus Vancomycin
NO	YES	YES	NO	YES	n/a	Clindamycin	Levofloxacin plus Clindamycin or Vancomycin	Levofloxacin plus Clindamycin or Vancomycin	Levofloxacin plus Vancomycin
NO	YES	YES	YES	NO	n/a	Levofloxacin plus Clindamycin or Vancomycin	Levofloxacin plus Clindamycin or Vancomycin	Levofloxacin plus Vancomycin	Levofloxacin plus Vancomycin
NO	YES	YES	YES	YES	n/a	Levofloxacin plus Clindamycin or Vancomycin	Levofloxacin plus Clindamycin or Vancomycin	Levofloxacin plus Vancomycin	Levofloxacin plus Vancomycin
YES	NO	NO	NO	NO	Amoxicillin or Amoxicillin/Clavulanate	Ampicillin or Ceftriaxone	Ampicillin or Ceftriaxone	Ceftriaxone	Ceftriaxone plus Vancomycin
YES	NO	NO	NO	YES	Amoxicillin/Clavulanate or Clindamycin	Ampicillin/Sulbactam or Clindamycin	Ampicillin/Sulbactam or Clindamycin	Ampicillin/Sulbactam or Clindamycin	Ceftriaxone plus Vancomycin

YES	NO	NO	YES	NO	n/a	Ceftriaxone plus Clindamycin or Vancomycin	Ceftriaxone plus Clindamycin or Vancomycin	Ceftriaxone plus Vancomycin	Ceftriaxone plus Vancomycin
YES	NO	NO	YES	YES	n/a	Ceftriaxone plus Clindamycin or Vancomycin	Ceftriaxone plus Clindamycin or Vancomycin	Ceftriaxone plus Vancomycin	Ceftriaxone plus Vancomycin
YES	NO	YES	NO	NO	n/a	Ampicillin or Ceftriaxone	Ceftriaxone plus Clindamycin or Vancomycin	Ceftriaxone plus Clindamycin or Vancomycin	Ceftriaxone plus Vancomycin
YES	NO	YES	NO	YES	n/a	Ampicillin/Sulbactam or Clindamycin	Ceftriaxone plus Clindamycin or Vancomycin	Ceftriaxone plus Clindamycin or Vancomycin	Ceftriaxone plus Vancomycin
YES	NO	YES	YES	NO	n/a	Ceftriaxone plus Clindamycin or Vancomycin	Ceftriaxone plus Clindamycin or Vancomycin	Ceftriaxone plus Vancomycin	Ceftriaxone plus Vancomycin
YES	NO	YES	YES	YES	n/a	Ceftriaxone plus Clindamycin or Vancomycin	Ceftriaxone plus Clindamycin or Vancomycin	Ceftriaxone plus Vancomycin	Ceftriaxone plus Vancomycin

## Appendix 2

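### EOM 4.1 is labelled a proxy for treatment failure but counts any different antibiotic after 72 hours, so narrowing and drug-changing step-down count as failures

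*SAP*

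**What the plan says.** SAP 2.3 states exploratory objective EO 4 as "To compare the changes in antibiotics, used as a proxy for treatment failure, after 72 hours". SAP 4.3 makes this operational as the "Proportion of participants with different antibiotic(s) or changing treatments from no-antibiotic(s) to antibiotic(s), used as a proxy for treatment failure, after 72 hours". SAP 10.3(d) repeats that "the proportion of participants with different antibiotic(s) or changing treatments from no-antibiotic(s) to antibiotic(s) after 72 hours is the outcome" and borrows the EO 2 analysis: a chi-square test, proportions and their difference with 95% confidence intervals, and a mixed effects logistic model.

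None of these places restricts the change by direction, route or reason. Protocol 7.2 lists changes in antibiotics after 72 hours among the exploratory outcomes, without a definition and without the failure label. No other Phase 1 outcome carries that label.

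The starting point of the 72 hours is not stated for this measure. Protocol 7.2 does anchor the primary outcome's window: "For hospitalized patients, this will include therapy received during the first 24 hours of care beginning with ED triage".

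**The concern.** A proxy for failure should rise when treatment fails. The second limb of EOM 4.1, from no antibiotic to an antibiotic, does that. The first limb, a different antibiotic, also captures the opposite event: an improving child whose treatment is narrowed, or who changes to a different oral drug.

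The intervention promotes guideline-concordant, narrower initial therapy, and in some young children watchful waiting. Whether that approach needs rescuing during treatment is a natural safety question, and EOM 4.1 is the measure labelled to address it. If many of its events are planned narrowing, a null result could be read as reassurance that the data do not provide.

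The frequency of such changes could also depend on arm. The intervention aims to change the starting drug, and on the ward "the tool will advise consideration of oral therapy in children with good oral intake".

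**Working it through.** **What counts under the present wording**

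- Ceftriaxone to ampicillin or amoxicillin after 72 hours: a different antibiotic, so an event.
- An intravenous drug to a different oral drug: an event.
- Clindamycin or levofloxacin changed from intravenous to oral: same drug, so not an event.
- Ampicillin to amoxicillin: unclear. Protocol Table 1 pairs them as one ward entry, but only for concordance, and the SAP does not carry the pairing into EOM 4.1.

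**Formula check.** The plan gives no figure for EOM 4.1. To confirm that the power formula matches the plan's method, I applied it to the Phase 1 primary outcome (SAP 6.2.1: 750 per arm, 30% in usual care, detectable difference 6.8 points, alpha 0.05, 80% power). A two-sided, two-proportion z test of 30% vs 36.8% needs 754 per arm, and 750 per arm gives 79.8% power. The stated figure reproduces.

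**Inputs for the illustration**

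- Per arm: n = 750, or the plan's conservative effective 500 (SAP 6.2.1).
- Admission share: a = 0.31, range 0.19 to 0.69. This is from a 35-hospital study cited in Protocol 1.0, and applying it to the trial sites is an assumption.
- True escalation: f = 3% usual care vs 6% intervention. Assumed.
- Share of hospitalised children narrowed after 72 hours: r = 10%, 25% or 50%, equal in both arms. Assumed.
- Upper limit on r: Protocol 2.0 reports that one-third of hospitalised children in the prior study stayed under 48 hours. At most about two-thirds could then be switched after 72 hours in hospital or at discharge. The true limit is lower, because children leaving between 48 and 72 hours also drop out. At r = 50%, 0.50 / 0.667 = 75% of those staying 48 hours or more would have to be narrowed, so that column is an upper case.

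**Formulas**

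- Added events per participant: d = a × r. Observed rates: p0 = 0.03 + d and p1 = 0.06 + d (no overlap).
- Odds ratio = p1(1 − p0) / [p0(1 − p1)].
- 95% CI half-width = 1.96 × √{[p0(1 − p0) + p1(1 − p1)] / n}.
- Power = Φ{[(p1 − p0) − 1.96 √(2p̄(1 − p̄)/n)] / √([p0(1 − p0) + p1(1 − p1)]/n)}, where p̄ is the mean of p0 and p1.

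Worked case, r = 25%, n = 750: d = 0.31 × 0.25 = 0.0775, p0 = 0.1075, p1 = 0.1375, p̄ = 0.1225. The two standard errors are 0.01693 and 0.01691. Power = Φ[(0.03 − 0.03318) / 0.01691] = Φ(−0.188) = 43%.

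| | r = 0 | r = 10% | r = 25% | r = 50% |
|---|---|---|---|---|
| Added per 100 participants | 0 | 3.1 | 7.8 | 15.5 |
| Observed rates, % | 3.0 vs 6.0 | 6.1 vs 9.1 | 10.8 vs 13.8 | 18.5 vs 21.5 |
| Difference, points | 3.0 | 3.0 | 3.0 | 3.0 |
| CI half-width at 750, points | 2.09 | 2.68 | 3.31 | 4.05 |
| Odds ratio | 2.06 | 1.54 | 1.32 | 1.21 |
| Power, 750 per arm | 80% | 59% | 43% | 31% |
| Power, 500 per arm | 63% | 43% | 30% | 22% |

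**Sensitivity, 750 per arm**

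- Other true rates: 2% vs 4% gives power 62%, 37%, 24% and 17% across the columns. 5% vs 8% gives 65%, 51%, 38% and 29%.
- Admission share: 19% with r = 10% still gives only 66%. 69% with r = 50% gives 22%.
- Overlap: if narrowing and escalation occur independently in the same children, the difference becomes 0.03 × (1 − d) = 2.9, 2.8 or 2.5 points. Hence roughly, not exactly, preserved.

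**Unequal narrowing (assumed rates, a = 0.31)**

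- 20% of hospitalised usual-care children and 10% of hospitalised intervention children: 3 + 6.2 = 9.2% vs 6 + 3.1 = 9.1%. The true excess of 3 points disappears.
- The reverse, 10% and 20%: 3 + 3.1 = 6.1% vs 6 + 6.2 = 12.2%. The excess roughly doubles.

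**The case against.** Several points on the other side stand.

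- A reader might infer that the definition dilutes any real difference. For the estimate that the SAP plans to report, it does not. Under equal narrowing the difference in proportions stays at or near 3 points, and the loss is in precision, power and the odds ratio.
- A reader might infer that all IV-to-oral step-down counts as failure. Only a change of drug clearly does.
- A reader might infer that the SAP contradicts itself. In the Appendix 1 row for prior beta-lactam use with no other risk factor, ceftriaxone is an inpatient option and "Amoxicillin or Amoxicillin/Clavulanate" is the outpatient entry. A ward child sent home on amoxicillin could then satisfy SOM 1.1 ("Proportions of participants exclusively using of concordant antibiotic therapy for the entire episode") and still fail EOM 4.1. That needs the outpatient column to govern an admitted child's discharge prescription, which neither document says. Concordance and change of regimen are also different constructs, so being positive on both is no contradiction.
- The rates of escalation and narrowing are assumptions, and the plan claims no power for this outcome.
- EOM 4.1 is one of six exploratory measures. ED revisits and hospitalizations at 72 hours and 7 days, death and delayed ICU transfer also bear on harm, so a null result here would not stand alone.

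These points reduce the weight of the concern without removing it. Calling the measure a proxy concedes imperfection, but the wording still counts improvement as failure. The other harm measures do not record escalation of antibiotics on the ward.

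**Conclusion.** The point holds as a minor one. As written, EOM 4.1 counts narrowing and drug-changing step-down after 72 hours as treatment failure. This is a stated rule rather than a gap in the text.

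If such changes are equally frequent in the two arms, the cost is precision. In the illustration the CI half-width rises from 2.09 to between 2.68 and 4.05 points, and power at 750 per arm falls from 80% to between 59% and 31%. All of this rests on assumed escalation and narrowing rates and on an admission share taken from outside the trial sites.

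If the frequencies differ by arm, the estimate is biased. That is plausible given what the intervention does. A reader might go on to infer that the bias favours the intervention, because usual care starts broader and has more to narrow. The documents do not support a direction: more drug-changing step-down in the intervention arm would push the other way, and no switching rates are given.

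The primary analysis is unaffected.

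**What to change.** In SAP 4.3 and 10.3(d):

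- Define EOM 4.1 as escalation from the initial regimen more than 72 hours after ED triage. Escalation means starting an antibiotic after none, adding an agent, or changing to a broader agent on a list fixed before analysis.
- State that narrowing and IV-to-oral step-down, such as ampicillin to amoxicillin, do not count.
- Flag changes made for an identified pathogen, since these need not mean failure.
- Keep the present any-change measure as a descriptive row by arm, so that lateral switches made for non-response remain visible.

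The cost is SAP wording and a coding rule. SAP 7.1 already collects medication orders and prescriptions, including route, and allows manual record review where needed. The study clinicians must agree the list and a rule for unclear switches, such as ceftriaxone to an oral cephalosporin, and those cases need limited chart review. Changes prescribed outside the two institutions may be missed, as they would be now. No new data, visits or participants are required.
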